### THE RECRUITMENT/ENROLLMENT PROCEDURES ARE THE SAME ON THE INTERVENTION AND CONTROL UNITS.

#### II. Intervention

#### FOR CONSENTED PATIENTS ON THE INTERVENTION UNITS:

The research nurse will provide Component III, the FamPath Care Pathway: 1) Information to the patient and family caregiver on the admitting condition, diagnostics, and treatment; 2) Family/patient education: provided in lay terms (cueing and motivating techniques, support of physical activity, meals, cognitive stimulation, behavioral support, and safety, provided in written and CD format) linked to joint family CG/nurse assessment (baseline cognition, physical function and social profile); 3) Jointly developed bedside goals and treatment plans (updated daily); discharge checklist; and 4) Coaching of primary nurse to communicate and provide a copy of the FamPath plan to post-acute providers.

The FamPath Care Pathway is initiated and continues throughout the hospitalization; it will vary based upon the patient's length of stay. In addition, 5) post-acute follow-up will provide ongoing education and modification of the function-focused care plan (phone contact within 72 hours of discharge, weekly telephone calls for a total of 7 additional weeks, then monthly for 4 months), coaching of CGs to communicate FFC goals and expectations to the post-acute providers as indicated.

The research nurse will also provide **Component IV (mentoring**) Assistance to champions and nurses on above consented patients to: a) complete the Physical Capability Assessments\*,  b) establish and update FFC goals with input from CGs/patients (Goal Attainment Scale\*)  and c) develop a care plan with family CG/ patient addressing factors that impede FFC (e.g., acute illness, sedation, pain, fear/anxiety, pain, apathy, NPS, depression) 2) Support to the unit champions to mentor and motivate nursing staff (RN, LPN, nursing assistants) by: (a) role modeling; (b) highlighting staff role models and positive opinion leaders; (c) garnering support by sharing success stories with nursing council and

administration; (d) maintaining Fam-FFC bulletin board with updates /educational reinforcement; and (e) observing nursing staff during care interactions using the Function Focused Care Behavior Checklist\*,  providing feedback to staff (See Tools).

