#### III. Data Collection

Patient data will be collected based on chart review, observations, actigraphy, and staff proxy informant interviews. Family CG data will be collected via electronic surveys on a tablet or by paper if a participant chooses. At all measurement time points, research evaluators will end data collection with the patient if he/she observes signs of dissent from the patient which includes: verbal refusal to answer a question, closing eyes and refusing to respond, asking the evaluator to leave, and moving away from the evaluator. The training of evaluators will include interrater reliability (minimum of 90%). Evaluators will not be informed of randomization results or provided with the details of the intervention. The research evaluators are fluent in Spanish and will use translated consents and study materials, in the event that Spanish is the primary language. The RedCap system will be used for screening of participants and data collection. The same data is collected on the intervention and control units. Descriptive (one-time) and outcome (multiple time-points) data are collected.

*Upon enrollment, within 48 hours of admission to the unit, patient and family CG descriptive measures* will be collected. Patient characteristics will include age, race/ethnicity, gender, marital status, education, medical diagnoses, medications, the use of sensory and mobility devices, and disease burden. Comorbid conditions will be classified with the *Charlson Comorbidity Index*.  Pre-admission function (ADL performance 2 weeks prior to admission) using the *Barthel Index*  (also an outcome measure) will be evaluated based on report from the family CG. Evaluation of hearing loss will be assessed using The Whisper Test. Pain will be measured using the Pain Assessment in Advanced Dementia and The Verbal Descriptor Scale. Upon discharge, length of stay, use of tethers (IV lines, pulse oximetry, urinary catheters, etc.), physical restraint use, and discharge disposition will be acquired. Cognitive *domains affected* by both dementia and delirium will be evaluated: executive function, orientation, memory, abstract thinking, and attention, evaluated by the subdomains of the *MoCA*.  The types of interventions provided on the FamPath assessment and care plan will be collected for descriptive purposes, extracted at the completion of the intervention.

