Depression	Cornell Scale for Depression in Dementia (CSDD) 	A 19-item survey designed to assess depressive symptoms in individuals with dementia. 154, 155 There is sufficient evidence of reliability and validity. 155	
NPS	Brief Neuropsychiatric Inventory (NPI-Q) 	A 12-item, reliable, validated informant-based assessment of neuropsychiatric symptoms and associated caregiver distress. 156	

Adverse Events	Report of falls, hospitalizations,	A monthly check of the patient hospital record to evaluate for
	transfers to the emergency	hospitalizations/ED visits (in addition to the family caregiver
	department	report at month 2 and month 6).

The following outcome measure data collection will be initiated within 72 hours of discharge (T1), and 2 month (T2) and 6 month post-discharge (T3), by research evaluators via interview of the patient/family CG

Family Caregiver Outcome Measures- collected for both control and intervention group.			
Aim 2: Evaluate the imp	Aim 2: Evaluate the impact of Fam-FFC on Family CG-centered outcomes.		
	All measures are self-rated and will be initiated within: 72 hours of discharge (T1), 2 (T2) and 6 months post-discharge (T3). This data is collected via pen/paper tools completed by family CG.		
Measure	Measure Tool Description		
Preparedness for caregiving	Preparedness for Caregiving Scale 	An 8-item instrument that asks caregivers how well prepared they believe they are for multiple domains of caregiving: physical care and emotional support, setting up support services, dealing with the stress of caregiving. Items are rated 0 (not at all prepared) to 4 (very well prepared); shows very good reliability and internal consistency, 157 including in family CGs of hospitalized persons with dementia. 59	
Caregiver Strain	Modified Caregiver Strain Index (CSI) 	A 13-question tool that measures strain (financial, physical, social, psychological, and personal) related to care provision, with excellent internal consistency and reliability. 158,159	
Caregiver Burden	Zarit Burden Interview (ZBI-12)  short version	12-item tool that measures caregiver perception of burden has shown high internal consistency and discriminative ability in caregivers of persons with dementia. 160,161	
Desire to Institutionalize	Desire to Institutionalize Scale 	6-item scale with moderate reliability; Cronbach alpha = 0.694.162	

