Cost Outcomes Aim3: Evaluate the relative costs for Fam-FFC v. control condition; calculate health care cost (post-acute health care utilization) and total cost savings for Fam-FFC. We have developed cost-related data collection forms, specifically Activity Diaries, to help facilitate data collection for the champions, research nurse facilitators, and staff. These include staff and research nurse time and hours worked, training time (including replacement), supplies, and incentives. Post—acute utilization will be evaluated with a cumulative count of emergency room visits, number/days of hospitalizations, and long-term nursing home admissions six months after discharge, obtained from questioning of the family at each point of data collection. Health care unit charges and reimbursement rates will be obtained from yearly publications from the American Hospital Associations and other health data organizations.

Treatment Fidelity. Treatment fidelity will be evaluated with regard to delivery of the intervention, receipt, and

enactment as shown in Table 5. Assessment of Environment and Policy will be conducted by the Fam-FFC Research Nurse with champions as part of the intervention (See Component 1). Knowledge of Fam-FFC is a valid and reliable 15-item paper and pencil multiple choice exam that tests staff knowledge about Fam-FFC. The Goal Attainment Scale  evaluates attainment of up to four patient goals and will be completed by the Fam-FFC Research Nurse with input from CGs, champions, nursing staff, and other health care professionals who work with the patient. This will be reviewed at discharge and post-discharge data collection points. The FamPath Audit tracks delivery of FamPath and Family CG Activity Logs monitor CG involvement and agreement with the care plan. The Function Focused Care Behavior Checklist (FFC-BC) is a valid and reliable objective measure including a 19-item checklist reflecting nursing staff performance of Fam- FFC. Oversight of treatment fidelity will be provided by the co-investigator (BR) who will collaborate with the research team to ensure adherence to the study manual of operations and standardization across sites. See below for a comparison of treatment fidelity for treatment and control sites.

Treatment Fidelity (Bolded items: both treatment and control sites; items not bolded: treatment site only)		
Focus	Data (Appendix B)	Evidence of Treatment Fidelity

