#### 7.4.5 Blinding of the Test Article

Describe how the test article is blinded.

To ensure comparable samples in both the treatment and control condition participants will be blinded to treatment arm prior to consent, since the Fam-FFC treatment requires more effort that the control condition.

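### Aim 3 counts all health care use from family report alone, although a monthly hospital-record check already planned in both arms covers two of the three components

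*Combined protocol and SAP*

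**What the plan says.** The Cost Outcomes (Aim 3) paragraph of section 7.2 defines post-acute use as a "cumulative count of emergency room visits, number/days of hospitalizations, and long-term nursing home admissions six months after discharge". The only source it names for these counts is the family: they are to be "obtained from questioning of the family at each point of data collection". Section 8.3, Aim 3, multiplies each person's units of use by published unit costs, undertakes to avoid counting services twice, and again names no other source for the counts.

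The patient outcome table in section 7.2, which applies to both groups, has an adverse events row. It plans "A monthly check of the patient hospital record to evaluate for" hospitalisations and ED visits, on top of the caregiver's "report at month 2 and month 6". Nursing home admissions are not listed there. No section says whether this check feeds Aim 3.

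Three further statements bear on the quality of family report:

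- Section 7.4.5 says "participants will be blinded to treatment arm prior to consent" and describes no masking of participants after that.
- The data collection text in section 7.2 says "Evaluators will not be informed of randomization results or provided with the details of the intervention".
- Intervention families receive "phone contact within 72 hours of discharge, weekly telephone calls for a total of 7 additional weeks, then monthly for 4 months". The control description (sections 7.2 and 7.4.1) gives caregivers hospital orientation and reinforcement of discharge teaching, with no post-discharge call schedule.

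**The concern.** H4 predicts lower post-discharge cost under Fam-FFC and H5 predicts overall savings. Both rest on these counts, and section 1.2 lists health care cost and total cost savings among the primary endpoints. As written, the trial will hold two sources for ED visits and hospitalisations, will cost only one of them, and has no rule for the case where they disagree.

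Using only family report carries two risks:

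- **Equal under-reporting.** If families in both arms omit the same share of events, the ratio between arms is unchanged but the absolute cost difference shrinks by that share. H5 feels this most. Intervention costs are recorded through Activity Diaries, while the savings meant to offset them would be under-counted.
- **Unequal under-reporting.** The family is the respondent, so keeping evaluators unaware of allocation does not mask the answer. Different contact after discharge could change how well families remember events. That would produce a difference between arms where none exists, or hide a real one.

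**Working it through.** No figure in the plan depends on this point, so there is none to reproduce. The check sets the texts side by side and then sizes the problem on assumed values.

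**Coverage of the two sources**

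| Aim 3 component | Family questioning | Monthly record check |
|---|---|---|
| Emergency visits | yes | yes |
| Hospitalisations | yes | yes |
| Hospital days | yes | not stated whether abstracted |
| Long-term nursing home admissions | yes | not listed |

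**Recall interval.** T2 is at 2 months and T3 at 6 months, each with a two-week window either side (section 7.2). The nominal gap is 4 × 52/12 = 17.3 weeks. With T2 early and T3 late it is 17.3 + 2 + 2 = 21.3 weeks.

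**Scheduled post-discharge contacts.** Intervention: 1 + 7 + 4 = 12. Control: none stated.

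**Effect on the counts.** The documents give no capture rates, so these are assumptions. Let f be the share of true events that families report and r the share that the record shows. If the sources are independent, capture by either is 1 − (1 − f)(1 − r).

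- Family report alone, f = 0.90 in one arm and 0.80 in the other, with equal true use: 1 − 0.80/0.90 = 11% false difference.
- Adding a record with r = 0.70: capture is 1 − 0.10 × 0.30 = 0.97 and 1 − 0.20 × 0.30 = 0.94; 1 − 0.94/0.97 = 3%.
- Adding a record with r = 0.50: capture is 1 − 0.10 × 0.50 = 0.95 and 1 − 0.20 × 0.50 = 0.90; 1 − 0.90/0.95 = 5%.
- If every recorded event is also reported by the family, capture stays at 0.90 and 0.80 and the false difference stays at 11%.

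**Effect on a test.** As a rough guide, take a yes/no event over six months with equal true risk of 30-50% in both arms (assumed). Allowing for the plan's 20% attrition, 438/2 × 0.8 = 175 per arm; clustering is ignored. A two-sided 5% test then rejects about 9-16% of the time when reporting is 90% v. 80%, and about 26-48% at 90% v. 70%. The plan tests mean costs, not a yes/no event, so this shows scale only.

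**Matching burden.** Under independence, the share of events in both sources at f = 0.90 is 0.90 × 0.50 = 45% to 0.90 × 0.70 = 63%. Each of these that fails to match would be counted twice, so the matching rule matters.

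**The case against.** The strongest reply is that nothing here is a contradiction. The record check serves adverse event capture, and family questioning serves costing. Family report can cover all three components and care at any facility. The same data are collected in both arms by evaluators not told the allocation, and the control is an attention control with its own caregiver education. Combining sources is a refinement, and it can introduce error: the Aim 3 text describes cumulative counts and does not say that families give event dates, so poor matching could turn one admission into two.

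Much of this stands. It lowers the weight of the point and shapes the fix, but does not justify leaving a planned source unused. Possible gaps in the record are a reason to combine the sources rather than to ignore one.

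Some stronger readings are tempting but unsupported:

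- A reader might infer that the record check covers everything Aim 3 counts. It does not list nursing home admissions.
- A reader might infer that the record is the better data set outright. The plan does not say whether it includes care outside the participating hospitals.
- A reader might infer that families are known to be unmasked. That is a reasonable inference from section 7.4.5 and the differing contact, but no section says families are told their arm.
- A reader might infer that the extra calls push reporting one way, or that families attribute events differently. The calls are for education and care planning, the counts need no attribution, and the direction of any bias cannot be determined.
- A reader might take about 3% as the expected residual. It is the most favourable result within the assumed range.

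**Conclusion.** The concern holds for two of the three components. The plan costs ED visits and hospitalisations from family report alone and leaves a planned record check in both arms unused for that purpose. Family report may under-count, and may do so unequally by arm.

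The size is illustrative. On assumed reporting of 90% v. 80%, the false difference is 11%. It falls to about 5-3% with an independent record capturing 50-70% of events, and the gain shrinks towards nothing as the sources overlap. These results rest on assumed capture rates and, for the reduction, on independence.

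This is an inexpensive improvement to H4 and H5, not a flaw that invalidates the trial. H1 and Aims 1 and 2 are unaffected.

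**What to change.** In sections 7.2 and 8.3, state that:

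1. An ED visit or hospitalisation counts for Aim 3 if it appears in either the monthly record check or the family report.
2. Dates and length of stay come from the record where available, and the abstraction form collects them.
3. Families are asked for the facility and approximate date of each event.
4. Events are matched with a pre-stated date tolerance and discrepancy rule, applied by someone masked to arm, so that the commitment in section 8.3 against double counting is kept.
5. Long-term nursing home admissions stay on family report.
6. The Aim 3 analysis is repeated on family report alone as a sensitivity analysis.

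It would also help to state which hospitals the record check covers.

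The cost is modest data management, two extra items on the family form, and some residual matching error. No new record check is needed.

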#### 7.3 Duration of Participation

Describe the duration of an individual subject's participation in the study.

Six months (with a potential two week extra to complete data collection.)

## 7.4 Test Article(s) (Study Drug(s) and/or Study Device(s))

#### 7.4.1 Description

Provide a brief description of all test articles (drugs (including any foods and dietary supplements), devices and/or biologics used in the research including the purpose of their use and their approval status with the Food and Drug Administration (FDA). Include information about the form of the drug product (e.g., tablets, capsules, liquid).

The **experimental condition**, Fam-FFC, will be coordinated and implemented by a Family-centered Function Focused Care Nurse (Fam-FFC Nurse), who will work in the treatment units 20 hours a week for 14 months to implement the four components of the intervention. In addition, the sites will identify two members of the nursing staff from each unit (one for day and one for evening shift) to be Family-centered Function Focused Function Focused Care Champions (Fam-FFC Champions). The four components of Fam-FFC include: **Component I-** Environmental and Policy Assessments; **Component II-** Education and Training of Nursing Staff; **Component III-** Ongoing Training and Motivation of Nursing Staff. The Fam-FFC Nurse will work with the champions to mentor and motivate nursing staff (RN, LPN, nursing assistants) to provide Fam-FFC by: (a) role modeling Fam-FFC, reinforcing performance of and benefits of Fam-FFC, and brainstorming about ways to overcome challenges; (b) highlighting staff role models and

positive opinion leaders; and (c) eliminating the influence of negative opinion leaders; **Component IV** Implementation of the FamPath Care Pathway which includes: (a) information on the admitting condition, diagnostics, and treatment, (b) family/patient education, (c) transitional hand-off to post-acute providers, and (d) post-acute follow-up to provide ongoing education and modification of the function-focused care plan.

The Attention Control condition (Fam- FFC Ed-only) consists of Component II, education of the nursing staff in participating hospital units (exactly as offered in treatment sites), and education of CGs about hospital orientation and reinforcement of discharge teaching (medications/treatments, medical follow-up). Research staff not familiar with Components I, III and IV will deliver the staff and CG education per manualized protocol.

#### 7.4.2 Treatment Regimen

Describe dose, route of administration and treatment duration. Include information about dose adjustments.

The intervention begins during hospitalization. Post -acute follow-up will provide ongoing education and modification of the function-focused care plan (contact within 72 hours of discharge, weekly telephone calls for a total of 7 additional weeks, then monthly for 4 months).

## 7.4.3 Method for Assigning Subject to Treatment Groups

Describe the randomization process and how the associated treatment assignment will be made.

After the hospitals are randomized to the time cohort, within each six hospitals the two inpatient units will be randomly assigned so that one unit will receive Fam-FCC and the other unit will receive Staff-Ed (control) intervention. Random assignment will be completed by the statistician using SAS proc plan which specifically allows simultaneous randomization on multiple dimensions (time and units) as well as counterbalancing across units.

#### 7.4.4 Subject Compliance Monitoring

Insert the procedures for monitoring subject compliance.

Treatment Fidelity. Treatment fidelity will be evaluated with regard to delivery of the intervention, receipt, and enactment.  Assessment of Environment and Policy will be conducted by the Fam-FFC Research Nurse with champions as part of the intervention (See Component 1).  Knowledge of Fam-FFC is a valid and reliable 15- item paper and pencil multiple choice exam that tests staff knowledge about Fam-FFC.  The Goal Attainment Scale  evaluates attainment of up to four patient goals and will be completed by the Fam-FFC Research Nurse with input from CGs, champions, nursing staff, and other health care professionals who work with the patient. This will be reviewed at discharge and post-discharge data collection points. The FamPath Audit tracks delivery of FamPath and Family CG Activity Logs monitor CG involvement and agreement with the care plan. The Function Focused Care Behavior Checklist (FFC-BC)  is a valid and reliable objective measure including a 19-item checklist reflecting nursing staff performance of Fam- FFC. Oversight of treatment fidelity will be provided by the co-investigator (BR) who will collaborate with the research team to ensure adherence to the study manual of operations and standardization across sites.

#### 7.4.5 Blinding of the Test Article

Describe how the test article is blinded.

To ensure comparable samples in both the treatment and control condition participants will be blinded to treatment arm prior to consent, since the Fam-FFC treatment requires more effort that the control condition.

#### 7.4.6 Receiving, Storage, Dispensing and Return

#### 7.4.6.1 Receipt of Test Article

Describe how the test article will be obtained and from what source. Describe how the study test article will be packaged along with amounts (e.g., number of tablets/capsules or volume of liquid) and labeling. If drug kits are used, describe all the contents of the kit and associated labeling.

n/a

